3. DESCRIPTION OF DESIGN AND TRIAL POPULATION

3.1 OVERALL TRIAL DESIGN AND PLAN

This is a Phase I, non-randomized, uncontrolled, open-label, dose escalation trial of BI 836880 monotherapy and combination therapy of BI 836880 and BI 754091, which are administered intravenously every 3 weeks. The eligible patient population will be advanced solid tumours. The trial consists of two Parts; Part I (monotherapy part) and Part II (combination therapy part). Part II will commence after completion of Part I.

The data obtained from the trial will determine the MTD estimate based on a Bayesian logistic regression model with overdose control ([R13-4803](#)). The BLRM estimates the MTD by updating estimates of the probability of observing a DLT in the MTD evaluation period for each dose level in the trial as patient information becomes available. At any time in the trial, it will not be permitted to escalate to a dose which does not fulfil the escalation with overdose control (EWOC) principle (refer to Section [7](#)).

Successive cohorts of patients will receive increasing doses of BI 836880 single agent or combination of BI 836880 and BI 754091 until the MTD is reached or RP2D is determined. For any dose-escalation cohort, at least 3 patients will be required (refer to Section 7). However, in the case that only 2 patients are evaluable and neither has experienced a DLT within the MTD evaluation period, then dose-escalation can occur based on these 2 patients.

Doses may be de-escalated based on the occurrence of DLT and overall safety data. For the first cohort, 3 patients are planned to be treated. A cohort size of at least 3 patients will be treated at each subsequent cohorts. After all patients in a cohort have either experienced a DLT or have been observed for at least the MTD evaluation period without experiencing a DLT, the Bayesian model will be updated with the newly accumulated data. The overdose risk will then be calculated for each dose, and dose escalation will be permitted to all doses which fulfil the EWOC criterion and dose escalation rules according to Section [4.1.3](#). Decision on further recruitment (dose escalation, de-escalation or cohort expansion) will be made by the Safety Monitoring Committee (SMC) based on the collected safety data as well as other data when available. The doses will not exceed the RP2D established in the preceding trials in Western patients.

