4.1.3 Dose-finding scheme

The dose is planned to be tested in cohorts at pre-defined provisional dose levels. The provisional dose levels to be assigned to different cohorts of patients are listed in [Table 4.1.3:](#)

Proprietary confidential information © 2019 Boehringer Ingelheim International GmbH or one or more of its affiliated companies

1 and 4.1.3: 2. Intermediate or lower dose levels may be investigated if agreed in the SMC, depending on the number of DLTs observed in the trial.

In Part II, increasing doses of BI 836880 will be administered in combination with BI 754091 at 240 mg. The dose of BI 754091 may also be titrated based on DLTs and the overall safety profile of the combination.

Table 4.1.3: 1 Example of dose escalation in Part I*

Dose level	Proposed dose of BI 836880	Increment from previous dose
0	360 mg	Starting dose
1	720 mg*	100%

*Actual dose assignments for a cohort will be communicated separately as determined by the SMC. Intermediate dose level(s) may be investigated depending on the latest DLT rate estimate. Dose levels which are higher than the recommended dose in trial 1336-0001 (720 mg) will not be investigated.

Table 4.1.3: 2 Example of dose escalation in Part II*

Dose level	Proposed dose of BI 836880	Proposed dose of BI 754091	Increment from previous dose (BI 836880)
0	120 mg*	240 mg*	Starting dose
1	360 mg*	240 mg*	200%
2-a	500 mg*	240 mg*	39% (from 360 mg)
2-b	720 mg*	240 mg*	100% (from 360 mg)

*Actual dose assignments for a cohort will be communicated separately as determined by the SMC. Intermediate dose level(s) may be investigated depending on the latest DLT rate estimate. Dose levels which are higher than the recommended dose in trial 1336-0011 will not be investigated. For dose level 2, level 2-a or 2-b will be investigated based on the information from trial 1336-0011.

There will be no dose escalations of BI 836880 or BI 754091 in any one patient.

When the last patient in each cohort completes Cycle 1, the SMC will evaluate the available data. The SMC will review all safety data including, but not limited to, DLTs and all CTCAE Version 5 Grade ≥ 2 toxicity data during cycle 1. Updated safety data on other ongoing patients, including data beyond cycle 1, will be discussed as well. Based on that, a decision on the next dose level to be tested will be made.

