where $r_{d1,d2}$ denotes the variable describing the observed number of DLTs from $n_{d1,d2}$ patients at the dose combination d_1, d_2 .

Since a Bayesian approach is applied, prior distributions f for each of the parameter vectors $\theta_1 = (\log(\alpha_1), \log(\beta_1))$, $\theta_2 = (\log(\alpha_2), \log(\beta_2))$ and for the interaction term η need to be specified.

The prior distributions for θ_1 and θ_2 will be specified as mixtures of two multivariate normal distributions, i.e.

$$f(\theta_k) = a_{1,k} f_1(\theta_k) + a_{2,k} f_2(\theta_k)$$

with

$a_{1,k}, a_{2,k}$ the prior mixture weights, $k=1,2$ and

$$f_i(\theta_k) = \text{MVN}(\mu_{ik}, \Sigma_{ik}) \quad (k=1,2),$$

the multivariate normal distribution of the i -th component with mean vector μ_{ik} and covariance matrix Σ_{ik} , where

$$\Sigma_{ik} = \begin{pmatrix} \sigma_{ik,11}^2 & \sigma_{ik,11}\sigma_{ik,22}\rho_{ik} \\ \sigma_{ik,11}\sigma_{ik,22}\rho_{ik} & \sigma_{ik,22}^2 \end{pmatrix}$$

Mixture prior distributions have the advantage that they allow for specification of different logistic dose-toxicity curves, therefore making the prior more robust.

A meta-analytic approach will be used for the prior specification of η .

The estimated probability $\pi_{12,d1,d2}$ of a DLT at each dose combination d_1, d_2 from the model will be summarised using the following intervals:

Under dosing: [0.00, 0.16)

Targeted toxicity: [0.16, 0.33)

Over dosing: [0.33, 1.00]

The BLRM-recommended dose for the next cohort is the level with the highest posterior probability of the DLT rate falling in the target interval [0.16, 0.33) among the doses fulfilling EWOC. Applying the EWOC criterion it should be unlikely (<25% posterior probability) that the DLT rate at that dose will exceed 0.33.

As described The MTD may be considered to be reached if one of the following criteria is fulfilled:

1. The posterior probability of the true DLT rate in the target interval [0.16 – 0.33) of the MTD is above 0.5, OR
2. At least 9 patients have been treated in the study, of which at least 6 at the MTD.

Prior derivation:

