To determine the prior distributions for θ_1 , θ_2 and η a meta-analytic predictive (MAP) approach will be used. Toxicity information on BI 836880 monotherapy from the study 1336-0001, and the Part 1 of this study, toxicity information on BI 754091 monotherapy from the studies 1381-0001 and 1381-0004, and toxicity information on the combination of BI 836880 and BI 754091 from study 1336-0011 will be incorporated. Exact details on the evaluation of the model using hypothetical data scenarios and operating characteristics are provided in the statistical appendix; a brief description is given here.

The historical data for BI 836880 can be found in [Table 7.1.1: 1](#). For BI 754091, the historical data can be found in Tables [7.1.2: 2](#) and [7.1.2: 3](#). Expected historical data for the combination of BI 836880 and BI 754091 can be found in [Table 7.1.2: 4](#). Since data from 1336-0012 Part 1 and 1336-0011 were not yet available by the time of finalization of the CTP, data as is might be observed in future in these trials will be used as dummy data. This dummy data will be replaced by actual data as soon as it becomes available. Whenever BLRM calculations are performed for Part 2 of 1336-0012, all available information will be used and the resulting prior distribution will be documented.

Table 7.1.2: 1 Hypothetical data expected from 1336-0012 part 1

Dose BI 836880 (mg)	N of patients treated	N of patients with DLTs during MTD evaluation period
360	6	1
720	3	2

Table 7.1.2: 2 Preliminary data from 1381-0001

Dose BI 754091 (mg)	N of patients treated	N of patients with DLTs during MTD evaluation period
80	3	0
240	34	0
400	3	0

Table 7.1.2: 3 Preliminary data from 1381-0004

Dose BI 754091 (mg)	N of patients treated	N of patients with DLTs during MTD evaluation period
240	6	0

Table 7.1.2: 4 Hypothetical data expected from 1336-0011

Dose BI 836880 (mg) / BI 754091 (mg)	N of patients treated	N of patients with DLTs during MTD evaluation period
360 / 240	1	1
500 / 240	0	0
720 / 240	0	0

The following steps were performed to derive the prior distribution for Part 2:

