- 1) The meta-analytic predictive prior was derived for both compounds and for the interaction parameter η using the information in Tables 7.1.2: 1 – 7.1.2: 4, allowing for moderate to substantial between-trial heterogeneity, tau parameters are assumed to be normally distributed with mean $\log(0.25)$ and SD $\log(2)/1.96$. See a reference ([R18-3210](#)) for details on the MAP prior. These prior components were assigned 90% mixture weight for both compounds.
- 2) A second, weakly informative prior component was added with the same mean values as the MAP prior, standard deviation (2, 1) and correlation 0. This mixture component was assigned 10% mixture weight

The resulting parameters of the prior distributions for four combination levels, i.e., (120/240, 360/240, 500/240, 720/240), are given in [Table 7.1.2: 5](#). The corresponding prior probabilities of a DLT at different dose combinations and the corresponding probabilities of under toxicity, targeted toxicity and over toxicity are shown in [Table 7.1.2: 6](#). As can be seen from Table 7.1.2: 6, the dose combination 120 mg BI 836880 and 240 mg BI 754091 has prior probability of over toxicity below 25%. It fulfils the overdose criterion and is therefore a suitable starting dose combination.

Table 7.1.2: 5 Prior Distribution

Parameter	Prior distributions Means, standard deviations, correlation	Mixture weight
log(α_1), log(β_1): component 1	(-1.877,-0.574), (0.983, 0.893), -0.145	0.9
log(α_1), log(β_1): component 2	(-1.877,-0.574), (2,1), 0	0.1
log(α_2), log(β_2): component 1	(-1.500, 1,213), (1.070, 1.034), 0.387	0.9
log(α_2), log(β_2): component 2	(-1.500, 1,213), (2,1), 0	0.1
η	0.466, 0.989	N/A

Table 7.1.2: 6 Prior probabilities of DLTs

Dose (mg)	Dose (mg)	Probability of true DLT rate in			Descriptive statistics				
		[0,0.16)	[0.16,0.33)	[0.33,1]	Mean	SD	2.5%	50%	97.5%
BI 836880	BI 754091								
120	240	0.486	0.327	0.187	0.209	0.162	0.023	0.165	0.637
360	240	0.280	0.311	0.409	0.318	0.213	0.035	0.273	0.814
500	240	0.134	0.213	0.653	0.468	0.255	0.059	0.454	0.933
720	240	0.077	0.100	0.822	0.680	0.299	0.065	0.774	1.000

The prior will be updated once the trial has started in case new data that can be used will be available. The prior that is used for each BLRM analysis for the SMC meetings will be documented in the SMC minutes, the prior used for the final analysis will be documented in the TSAP.

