7.6 DETERMINATION OF SAMPLE SIZE

No formal statistical power calculations of sample size were performed. Approximately 9 patients for Part I are expected, and approximately 15 patients for Part II are expected. As

Proprietary confidential information © 2019 Boehringer Ingelheim International GmbH or one or more of its affiliated companies

more patients might be needed based on the recommendation of the SMC and the actual number of cohorts tested.

8. INFORMED CONSENT, TRIAL RECORDS, DATA PROTECTION, PUBLICATION POLICY, AND ADMINISTRATIVE STRUCTURE

The trial will be carried out in compliance with the protocol, the ethical principles laid down in the Declaration of Helsinki, in accordance with the ICH Harmonized Guideline for Good Clinical Practice (GCP), relevant BI Standard Operating Procedures (SOPs), the Japanese GCP regulations (Ministry of Health and Welfare Ordinance No. 28, March 27, 1997) and other relevant regulations. Investigators and site staff must adhere to these principles. Deviation from the protocol, the principles of ICH GCP or applicable regulations as will be treated as "protocol deviation".

Standard medical care (prophylactic, diagnostic and therapeutic procedures) remains the responsibility of the treating physician of the patient.

The investigator will inform the sponsor immediately of any urgent safety measures taken to protect the trial patients against any immediate hazard, as well as of any serious breaches of the protocol or of ICH GCP.

The Boehringer Ingelheim transparency and publication policy can be found on the following web page: trials.boehringer-ingelheim.com. The rights of the investigator and of the sponsor with regard to publication of the results of this trial are described in the investigator contract. As a rule, no trial results should be published prior to finalisation of the Clinical Trial Report. In exceptional cases, data may be published before the clinical trial report as long as this is discussed and agreed to by the investigators and the sponsor.

The certificate of insurance cover is made available to the investigator and the patients, and is stored in the ISF.

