Table 10.5.2: 2 Assumed true dose-toxicity scenarios

Scenario		Dose (mg)		
		120/240	360/240	720/240
1 (Prior)	P(DLT)	0.209	0.318	0.680
2 (High Tox)		0.291	0.327	0.516
3 (Low Tox)		0.054	0.128	0.190
4 (Non-Logistic)		0.145	0.290	0.505
5 (Low-High)		0.128	0.169	0.550
6 (Super High Tox)		0.489	0.580	0.769

Table 10.5.2: 3 Simulated operating characteristics

Scenario	% of trials declaring an MTD with true DLT rate in				# Patients	# DLT
	underdose	Target dose	overdose	STOPPED		
1	5.9	76.9	3.8	13.4	11.9 (3-30)	3.3 (1-10)
2	0.0	64.6	9.5	25.9	10.3 (3-30)	3.4 (1-11)
3	68.1	29.2	0.0	2.7	14.6 (3-42)	1.8 (0-8)
4	66.3	7.5	20.8	5.4	11.8 (3-27)	2.8 (1-9)
5	62.2	10.6	23.4	3.8	11.9 (3-27)	2.7 (1-7)

6	0.0	24.4	26.5	49.1	11.0 (3-27)	4.3 (1-10)
---	-----	------	------	------	-------------	------------

In scenario 1, which reflects the case that the true dose-toxicity is aligned with prior means, 76.9% of the simulated trials declared a dose as MTD with true DLT rate in the targeted dose range.

In Scenario 2 (high-toxicity scenario), 64.6% of the simulated trials declared a dose as MTD with true DLT rate in the targeted dose range.

In Scenarios 1 and 2, the starting dose has already >12.0% probability of observing at least 2 DLTs out of 3 patients or 1 DLT out of 2 patients in the first cohort. This contributes to the high percentage of all simulated trials for which the trial is stopped, since none of the doses is considered tolerable anymore. This is an expected situation for assumed dose-toxicity scenarios.

In Scenarios 3-5, there is/are one or two dose(s) with assumed true toxicity probability in the underdosing interval [0.00, 0.16), in some cases the model chooses that dose as MTD that is closest to the target interval, which results in certain percentage of trials with an MTD with true DLT rate in underdosing interval.

Scenario 6 shows that when the true DLT rate is super high, 49.1% of simulated trials stopped, since none of the doses is considered tolerable anymore. This is an expected situation for a super high-toxicity scenario.

The mean patient numbers range from 10.3 patients (Scenario 2) to 14.6 (Scenario 3) during simulation. This shows that the planned maximum of 12 patients is reasonable.

In summary, the considered data scenarios show a reasonable behaviour of the model and the operating characteristics demonstrate a good precision of MTD determination.

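### Part II operating characteristics (Table 10.5.2:3) do not belong to the doses listed in Table 10.5.2:2 and cannot support the good-precision conclusion

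*Protocol*

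**What the plan says.** Table 4.1.3:2 lists 120/240, 360/240 and a second level that is either 2-a (500/240) or 2-b (720/240): "For dose level 2, level 2-a or 2-b will be investigated based on the information from trial 1336-0011". Intermediate levels are also allowed.

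Section 7.1.2 recommends the dose with the highest target-interval probability among doses meeting EWOC (posterior probability of a DLT rate of 0.33 or more below 25%). The MTD may be considered reached when the target probability exceeds 0.5, or under criterion 2: "At least 9 patients have been treated in the study, of which at least 6 at the MTD". Section 7.6 states that "approximately 15 patients for Part II are expected"; Section 10.5.2 still speaks of a planned maximum of 12.

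The prior in Table 7.1.2:5 rests partly on hypothetical data from Part I and from trial 1336-0011. Section 7.1.2 says of these: "This dummy data will be replaced by actual data as soon as it becomes available". Section 3.1 adds that "Part II will commence after completion of Part I".

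Table 10.5.2:2 gives true DLT rates for 120/240, 360/240 and 720/240 only. Table 10.5.2:3 prints the selection rates, and the section ends by saying that "the operating characteristics demonstrate a good precision of MTD determination".

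**The concern.** Tables 10.5.2:1 to 10.5.2:3 are the protocol's evidence on how the Part II rule behaves. If the selection rates were produced on other doses, or could not arise under the written EWOC rule, the trial's safety committee and outside readers have no valid statement of how often Part II would find a target dose or stop early.

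The low-toxicity case matters most. The printed 29.2% suggests that a well-tolerated combination would reach its target dose in nearly a third of trials. Table 10.5.2:1, Scenario 4, already points the other way: after 0/3 at 120/240 and 0/3 at 360/240 the model stays at 360/240, where the probability of underdosing is 0.609.

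**Working it through.** **Step 1. Set the two tables side by side (no model needed).** The intervals are underdose below 0.16, target 0.16 to below 0.33, overdose 0.33 and above.

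| Scenario | True rates 120/360/720 (Table 10.5.2:2) | Printed (Table 10.5.2:3) | Possible on these doses? |
|---|---|---|---|
| 1 | 0.209 / 0.318 / 0.680 | 5.9% underdose | No: no dose is below 0.16 |
| 6 | 0.489 / 0.580 / 0.769 | 24.4% target | No: all doses are above 0.33 |
| 3 | 0.054 / 0.128 / 0.190 | 29.2% target | Only by declaring 720/240 |

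**Step 2. Reproduce the plan's prior.** Inputs are the compound rows of Table 7.1.2:5 (reading 1,213 as 1.213) with weights 0.9 and 0.1, η with mean 0.466 and SD 0.989, and reference doses 500 and 240 mg. The model in Section 7.1.2 is

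- logit π₁ = log α₁ + β₁ log(d₁/500) and logit π₂ = log α₂ + β₂ log(d₂/240);
- π⁰ = π₁ + π₂ − π₁π₂;
- odds(π) = odds(π⁰) × exp(η × d₁/500 × d₂/240).

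Monte Carlo, prior P(DLT rate ≥ 0.33):

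| Dose | Table 7.1.2:6 | Rows as labelled | Rows exchanged |
|---|---|---|---|
| 120/240 | 0.187 | 0.422 | 0.185 |
| 360/240 | 0.409 | 0.592 | 0.404 |
| 500/240 | 0.653 | 0.651 | 0.651 |
| 720/240 | 0.822 | 0.701 | 0.823 |

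Only the exchanged rows reproduce the table. Prior means then agree too: 0.208/0.317/0.468/0.682 against 0.209/0.318/0.468/0.680. The same prior tracks Table 10.5.2:1 to within about 0.01, for example 0.083 against 0.085 (Scenario 4) and 0.294 against 0.295 (Scenario 5). The compound labels in Table 7.1.2:5 therefore appear to be exchanged.

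**Step 3. Follow a DLT-free course.** P(overdose) after 0/3 at 120/240 and 0/n at 360/240, exchanged rows, EWOC limit 0.25:

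| n at 360/240 | Total patients | 500/240 | 720/240 |
|---|---|---|---|
| 3 | 6 | 0.387 | 0.690 |
| 6 | 9 | 0.296 | 0.638 |
| 9 | 12 | 0.242 | 0.605 |
| 12 | 15 | 0.208 | 0.584 |
| 30 | 33 | 0.142 | 0.552 |

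For 720/240 the minimum is about 0.55, near n = 30. More clean patients at 360/240 do not bring it near 0.25.

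500/240 first opens at 12 patients. It is then the recommended dose, with target probability 0.311 against 0.160 at 360/240. In Scenario 3 the chance of that run is 0.946³ × 0.872⁹ = 0.8466 × 0.2915 = 0.247. At 9 patients, 6 of them at 360/240, criterion 2 may already be met and 500/240 is still closed at 0.296.

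**Step 4. Simulate the written rule on 120/360/720.** Settings: cohorts of 3, no skipping of untested levels, Scenario 3. Stopping on either MTD criterion gave 39.5% at 120/240, 57.0% at 360/240, 0.0% at 720/240 and 3.5% stopped. The 720/240 share was also 0.0% with a fixed 15 patients and with a fixed 42.

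**Step 5. Sensitivity at the first decision.** With the rounded parameters, 360/240 after 0/3 at 120/240 gives 0.2535, where Table 10.5.2:1 prints 0.248, so the rule can flip there. Relaxing the limit to 0.256 restores the printed decision. Scenario 3 then gives 32.7% / 66.1% / 0.0%, with 1.3% stopped. 720/240 is still never given.

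**The case against.** **The prior is provisional.** Section 7.1.2 says so, promises actual data, and commits to documenting the prior used for each analysis. That stands, and asking for the prior to be replaced would add nothing. But the promise covers the prior. Nothing in the protocol or SAP text available commits to re-running the operating characteristics, and the precision claim is made in the present tense on the illustrative prior.

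**The simulations may have used a wider grid.** Amendment 2 removed the BI 754091 80 mg and 400 mg tables from Table 10.5.2:2, and its log lists no change to Table 10.5.2:3. The 29.2% may therefore include combinations no longer listed. This is a plausible inference, and it limits what can be said about the simulation code: a reader might infer that the code broke EWOC, and the documents do not show that. It leaves the point intact, because the printed results would then describe combinations that are no longer listed.

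**Level 2 is not shut.** A reader might infer that no DLT-free course opens level 2, or that Part II cannot test its top dose. The documents do not support either reading:

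- 500/240 is a listed level-2 option and opens at 12 patients, within the expected 15.
- 720/240 can open later through 500/240: P(overdose) is about 0.23 after 0/3, 0/12 and then 0/12 at 500/240.
- The MTD criteria say only that the MTD may be considered reached, the committee may add patients, and intermediate levels are allowed.

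**The reconstruction is not exact.** Because of the near-tie in Step 5, recomputed stopping rates vary widely with the first decision (Scenario 1: 41.7% at limit 0.25, 21.1% at 0.256; 13.4% printed). They are not used as a refutation here. The 0% for 720/240 does not depend on that tie.

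**Conclusion.** The concern holds in this form: Table 10.5.2:3 does not describe the design in Table 10.5.2:2, so it cannot carry the precision conclusion. The evidence is of two strengths.

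- **From the documents alone:** the 5.9% underdose in Scenario 1 and the 24.4% target in Scenario 6 are impossible on the listed doses.
- **From the reconstructed model:** Scenario 3 target selection on 120/360/720 is 0%, against 29.2% printed. This assumes the exchanged compound rows, cohorts of 3, no level skipping and the written EWOC limit.

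Under the same prior, 500/240 needs 12 DLT-free patients out of about 15. The 25% chance in Scenario 3 assumes that 0/3 at 120/240 opens 360/240, as Table 10.5.2:1 prints, and that criterion 2 is not used to stop at 9.

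These results concern the stated operating characteristics under an illustrative prior. They do not predict what Part II will do once actual data replace the dummy data.

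**What to change.** 1. Correct the compound labels in Table 7.1.2:5.
2. Before the first Part II cohort, when the dummy data are replaced as Section 7.1.2 already requires, re-run Tables 10.5.2:1 to 10.5.2:3 with the actual prior. Use the combinations that can currently be given, including 500/240, under the written EWOC and MTD criteria. State how criterion 2 is applied in the simulation.
3. Report after how many DLT-free patients each level-2 option satisfies EWOC, set against the expected 15, and reconcile that figure with the maximum of 12 in Section 10.5.2.
4. Until then, withdraw the precision sentence. State instead that, under the illustrative prior, 720/240 is not reachable directly from 360/240 and that Table 10.5.2:3 does not apply to the listed doses. A flat statement that 720/240 cannot be reached would be wrong.

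The cost is one re-run of existing simulation code plus amended tables and wording, with no extra patients. The downside is that the stated Part II operating characteristics will look less favourable, at least until the actual prior is available.
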